1.0 BACKGROUND & STUDY RATIONALE

Extensive mitral annular calcification (MAC) poses a significant risk in elderly subjects undergoing mitral valve surgery. MAC has been associated with higher risk of cardiovascular disease, cardiovascular death, and all-cause death.¹ Surgical replacement of such valves presents a technically challenging procedure with the potential for rupture at the atrial ventricular junction and of the left ventricular wall.² Thus, new surgical and minimally invasive techniques for mitral replacement could improve treatment of high-risk subjects with MAC.

Recently, isolated reports of deployment of the Edwards SAPIEN[™] XT (Edwards Lifesciences, Irvine, CA, USA) valve in native mitral valves with extensive MAC have shown early anecdotal feasibility in a limited number of cases. There are several reports using transapical, transeptal, or transatrial approaches with varying degrees of success.^{3,4,5,6} The multi-center IDE Mitral Implantation of TRAnscatheter vaLves in native mitral stenosis (MITRAL) Study initiated by Northshore University Health System is currently studying this technique, primarily focusing on the transcatheter, transseptal approach. Early experience with this procedure demonstrates limited success with treatment of subjects with mitral stenosis and regurgitation associated with extensive MAC. However, technical challenges with this approach have included left ventricular outflow tract (LVOT) obstruction (11% of subjects), valve embolization (7%), and a 30-day mortality (34%) in the limited data available.⁷ In order to possibly mitigate some of the challenges with this approach, we propose to study a limited access surgical approach with the Edwards SAPIEN 3 valve placed in the mitral valve position under direct vision to optimize procedural safety and success. From our own limited experience with the successful treatment of 3 subjects with this approach is warranted.

2.0 DESCRIPTION OF STUDY PROCEDURE

Surgical access is allowed via any accepted heart team approach. Any commercially approved delivery system for the SAPIEN 3 valve may be used.

Surgical access is via a mini-anterolateral thoracotomy with the patient under general anesthesia and on February 26, 2016 Page 4 of 57 Protocol Version 1.1

SITRAL

Confidential

Baylor Scott & White Research Institute

cardiopulmonary bypass support. Cannulation for cardiopulmonary bypass is typically achieved through the common femoral arterial and venous circulation, though axillary arterial cannulation is a suitable substitute for subjects in which there is concern for arterial occlusive disease. There are several methods to prepare for cardiac entry. These include a cardioplegic or cold, fibrillatory arrest, depending on the individual patient circumstances. A left atriotomy is performed to access the mitral valve. The mitral valve is then evaluated to determine whether conventional replacement is a reasonable depending upon the severity of MAC. If not, the anterior leaflet is then resected, leaving approximately 0.5cm to 1cm of residual leaflet tissue adjacent to the annulus. Pledgetted mattress sutures are placed in both of the fibrous trigones and the mid-portion of the posterior leaflet. The valve is then sized with a 25ml valvuloplasty balloon. If there is a reasonable fit with no gap between the inflated balloon and the annulus, then a 26mm Edwards SAPIEN 3 is selected. If there is a gap, then a 29mm Edwards SAPIEN 3 is selected. If there are concerns about the native annulus being too large, a cuff of felt material can be placed to minimize paravalvular leak.

The valve implant is performed with thoracoscopic guidance (30 degree, 5mm-10mm endoscope). The commisures of the prosthetic valve are aligned with the fibrous trigones. To control the delivery, two separate operators are required. One slowly delivers the valve correcting for depth and orientation while the other inflates the balloon slowly within the native valve to maximal dilation for at least 10 seconds, and thoracoscopic confirmation of a fully deployed valve is obtained. The fibrous trigone sutures are then placed through the skirt on the prosthetic valve and tied. The valve is tested with cold saline to ensure appropriate leaflet mobility and assess for paravalvular leak. Following confirmation, a vent may be placed across the valve for de-airing, and the atrium is closed.

3.0 PURPOSE

The purpose of this study is to establish the safety and feasibility of the Edwards SAPIEN 3 valve in subjects with mitral annular calcification (MAC) associated with mitral stenosis (MS) and/or mitral regurgitation who are at high-risk for mitral valve surgery or deemed inoperable due to the extent of calcification.

SITRAL

4.0 STUDY DESIGN

Baylor Scott & White Research Institute

Confidential

This is a multi-center, prospective feasibility study. The study cohort will comprise all consecutive subjects undergoing mitral valve replacement with the Edwards SAPIEN 3 heart valve by a standardized minimally invasive surgical approach at investigational centers and will consist of up to 30 subjects. Subjects will undergo follow-up visits at 30 days, 6 months and 12 months post procedure.

5.1 STUDY POPULATION

The study cohort will consist of up to 30 subjects who are candidates for mitral valve replacement using the Edwards SAPIEN 3 heart valve as per the inclusion and exclusion criteria below:

5.2 Inclusion Criteria:

- Subject has severe native mitral annular calcification associated with mitral stenosis and/or regurgitation. Qualifying echo must be within 60 days of the date of the procedure.
- Subject has a clinical indication for mitral valve replacement, as demonstrated by reported New York Heart Association (NYHA) Functional Class II or greater.
- The subject is at least 22 years old.
- The Heart Team agrees that the subject is high-risk or inoperable for surgical mitral valve repair or replacement (MVR), based on a conclusion that the probability of death or serious, irreversible morbidity exceeds the probability of meaningful improvement. The following concomitant procedures, are allowed MAZE, TVP, and AF ablation.
- The study subject has been informed of the nature of the study, agrees to its provisions and has provided written informed consent as approved by the Institutional Review Board (IRB) of the respective clinical site.
- The study subject agrees to comply with all required post-procedure follow-up visits

5.3 Exclusion Criteria

 Evidence of an acute myocardial infarction (MI) ≤ 30 days before the intended treatment [defined as: Q wave MI, or non-Q wave MI with total CK elevation of CK-MB ≥ twice normal in the presence of MB elevation and/or troponin level elevation (WHO definition)].

- Untreated coronary artery disease in need of revascularization
- Any therapeutic invasive cardiac procedure resulting in a permanent implant that is performed within 30 days of the index procedure (unless part of planned strategy for treatment of concomitant coronary artery disease).
- Leukopenia (white blood cell count < 2000 cell/mL), acute anemia (hemoglobin < 8 g/dL), or thrombocytopenia (platelet count < 50,000 cell/mL).
- Hemodynamic or respiratory instability requiring vasoactive medications, mechanical ventilation at time of procedure.
- Need for emergency surgery for any reason.
- Severe left ventricular dysfunction with Left Ventricular Ejection Fraction (LVEF) < 30%.
- Severe right ventricular dysfunction
- Pregnancy, lactation, or planning to become pregnant
- Echocardiographic evidence of left ventricular mass, thrombus, or concerns of active infective endocarditis.
- Active upper GI bleeding within 3 months prior to procedure without treatment or 30 days prior to procedure with definitive treatment.
- A known contraindication or hypersensitivity to all anticoagulation regimens, or inability to be maintained on oral anticoagulant following the study procedure.
- An estimated Glomerular Filtration Rate (eGFR) <30 as calculated using the Modification of Diet in Renal Disease (MDRD) formula or End stage renal disease requiring dialysis
- Clinically (by neurologist) or neuroimaging confirmed stroke or transient ischemic attack (TIA) within 30 days of the procedure.
- Estimated life expectancy < 12 months

6.0 STUDY OBJECTIVES

6.1 **Primary Outcome Measures:**

- a. Primary objective(s)
 - Primary safety endpoints:

- o Technical success at exit from cath lab/OR
- Device success at 30 days
- Procedural success at 30 days

Technical Success:

- Alive, with
- Successful access, delivery and retrieval of the device delivery system, and
- Deployment and correct positioning (including repositioning/recapture if needed) of the single intended device, and
- No need for additional unplanned or emergency surgery or re-intervention related to the device or access procedure

Device Success:

- Alive and stroke free, with
- Original intended device in place, and
- No additional surgical or interventional procedures related to access or the device since completion of the original procedure (i.e., exit from the cath lab/OR), and
- Intended performance of the device:
 - Structural performance: No migration, embolization, detachment, fracture, hemolysis, thrombosis (including reduced leaflet motion) or endocarditis, etc, and
 - Hemodynamic performance: Maintenance of relief of stenosis or insufficiency without producing the opposite (Stenosis = MVA < 1.5cm2 and MV gradient > 5mmHg, Insufficiency = MR >1+), and
 - Absence of para-device complications (e.g., PVL > mild, need for a PPM, erosion, Annular rupture or AV Groove disruption, LVOT gradient increase > 10mmHg)

Procedural Success:

Device success, and

- No device or procedure related SAE's (Life threatening bleed; major vascular or cardiac structural complications requiring unplanned reintervention or surgery; stage 2 or 3 AKI (includes new dialysis); MI or need for PCI/CABG; severe HF or hypotension requiring IV inotrope, ultrafiltration or mechanical circulatory support; prolonged intubation (> 48 hours)
- •
- 6.2 Secondary objective(s)
 - Device Success (at 6 months and 1 year)

- Subject success 1 year Device Success:
- Alive and stroke free, with
- Original intended device in place, and
- No additional surgical or interventional procedures related to access or the device since completion of the original procedure (i.e., exit from the cath lab/OR), and
- Intended performance of the device:
 - Structural performance: No migration, embolization, detachment, fracture, hemolysis, thrombosis (including reduced leaflet motion) or endocarditis, etc, and
 - Hemodynamic performance: Maintenance of relief of stenosis or insufficiency without producing the opposite (Stenosis = MVA < 1.5cm2 and MV gradient > 5mmHg, Insufficiency = MR >1+), and
 - Absence of para-device complications (e.g., PVL > mild, need for a PPM, erosion, Annular rupture or AV Groove disruption, LVOT gradient increase > 10mmHg)

7.0 STUDY METHODS

Methods for required study activities in the clinical investigational plan (CIP) are specified in the following subsections. Deviations from the CIP must be documented and reported to the Sponsor. All subjects must sign an IRB approved informed consent prior to performing any study activities described in this CIP.

Study data supporting enrollment eligibility must be recorded on the applicable case report forms. Source documentation supporting all case report form entries must be maintained at the investigational site and copies of source documents may be maintained by the Sponsor to support monitoring activities.

Investigators are expected to complete all applicable case report forms within 5 business days of the related follow-up visit or study activity. To ensure CIP compliance, data integrity, and protection of Subjects' rights, safety and welfare, Sponsor or its representative and other regulatory agencies may monitor the conduct of the study.

8.0 SUBJECT CONFIDENTIALITY

All Subject information collected during the study is kept strictly confidential. All data and information pertaining to the Subject and their participation in the study are considered confidential by Sponsor. All public reporting of study results must eliminate references to individual subjects. Information contained in paper form must be stored in secure areas. Electronic information that is kept on computers must be protected by secure passwords.

9.0 ENROLLMENT AND SCREENING

In order to protect the rights and welfare of subjects, the study is conducted in accordance with the 21 CRF 50, Protection of Human Subjects. All subjects are required to sign and date an IRB approved consent prior to participation in the study. All Subjects who sign an informed consent are assigned a unique identification number in order to maintain Subject traceability.

If during the course of the preoperative evaluations, the subject is found to be ineligible for study participation, the subject will be notified, and the reason for ineligibility will be documented on the Screening Log. Ineligible subjects are considered screen failures, and they will not be counted towards total enrollment and their subject ID number will not be reused. Sites are not required to enter data into the EDC system for any screen failures.

After screening assessments are made, the study candidate's qualifying criteria will be presented via the case review process where experienced study investigators will review the submitted criteria. Upon case review approval, the supporting evidence for approval and the names of the reviewer(s) will be

Page 10 of 57

documented. Once the review and the eligibility criteria are documented, the subject can be enrolled in the study.

Subjects are considered enrolled at the time of initial skin incision.

10.0 BASELINE FUNCTIONAL ASSESSMENTS

Functional Assessments such as 6 minute walk test (6MWT), NYHA classification, Quality of Life (QOL) assessments (Kansas City Cardiomyopathy Questionnaire [KCCQ]) and 5 meter walk test are collected as part of the screening activities for baseline comparative purpose against scheduled follow-ups post-procedure.

11.0 ANTICOAGULATION MEDICATION

Subjects should be maintained on a once daily dose of warfarin (Coumadin) for a minimum of 3 months post study procedure to maintain an international normalized ratio (INR) of between 2.5 and 3.5. If a subject is not eligible for warfarin, the subject should be maintained on appropriate anticoagulation per investigator. If the subject was on novel oral anticoagulation (NOAC) pre-study procedure, that medication may be continued in lieu of warfarin at the investigators discretion.

12.0 STUDY DEVICES

Investigators selected to participate in the study will have prior experience with Edwards SAPIEN 3 system. The Edwards SAPIEN 3 valve is approved by the Food and Drug Administration (FDA). The study sites will be authorized to utilize devices for the study procedure after receiving IRB approval and signing the clinical study agreement.

13.1 PREGNANCY TESTING AND CONTRACEPTION

13.2 Pregnancy Testing

A Woman of Child Bearing Potential (WOCBP) who is planning pregnancy should not participate in the study. For participation in this study, pregnancy has to be excluded in any female study participant below age 60.

13.3 Contraception

WOCBP (Women of Child Bearing Potential) who are considering participation in the study must be informed about the study related risks to pregnancy/embryonic development and must receive contraceptive counseling. WOCBP must agree to use effective contraception while participating in the study.

Female subjects who are considered WOCBP and who are engaging in intercourse with a male partner(s), must begin using an acceptable method of contraception as soon as feasible prior to enrollment and must continue throughout the duration of their study enrollment

13.4 Female subjects are considered non-WOCBP if they are either:

- A. Post-menopausal (12 months of natural (spontaneous) amenorrhea with an appropriate clinical profile (e.g., age appropriate, history of vasomotor symptoms) or six months of spontaneous amenorrhea with serum FSH levels > 40 mIU/mL)
- B. Have had surgical bilateral oophorectomy (with or without hysterectomy) at least six weeks prior to enrollment into the study. In the case of surgical bilateral oophorectomy only, this will only be acceptable when the reproductive status of the woman has been confirmed by a follow up hormone level assessment

14.1 ENROLLMENT AND STUDY PROCEDURES

14.2 Baseline/Screening

The following information will be collected for all study subjects prior to procedure. Baseline assessments must be completed within 30 days of subject enrollment unless otherwise specified. Subjects are considered enrolled at the time of initial skin incision.

- A. Society of Thoracic Surgeons (STS) Risk Score Assessment
- B. Medical History and Physical Exam including Cardiac Medications
- C. Cardiopulmonary:
 - 1. Cardiac Catheterization (within 6 months prior to consent)
 - 2. 3D Computed Tomography scan with contrast of chest, heart and peripheral vasculature with assessment of degree and pattern of MAC
 - 3. Transthoracic echocardiogram (TTE)
 - 4. 12 Lead Electrocardiogram (ECG)
 - 5. Chest X-Ray
 - 6. Pulmonary Function Test (PFT) within 1 year prior to consent
- A. Functional Assessments:
 - 1. 6 minute walk test (6MWT)
 - 2. NYHA classification
 - 3. QOL assessments: KCCQ
 - 4. 5 meter walk test (5MWT)
- B. Subject Clinical Laboratory Tests
 - 1. Complete Blood Count (CBC) and platelet count
 - 2. Complete metabolic panel (CMP) including Albumin
 - 3. B-type natriuretic peptide (BNP)
 - 4. PTT or PT/INR (if applicable)

5. A blood or urine pregnancy test will be performed at screening for females with childbearing potential. A positive pregnancy test will render the subject ineligible for study participation.

14.3 Intra-Procedure Assessments

Total procedure time is defined as the time from skin incision to the time of skin incision access closure. The following invasive hemodynamic data must be collected pre and post implant:

- A. Transesophageal echocardiogram (TEE) assessments:
 - 1. To be collected prior to placement of valve
 - i. Mitral valve gradient (peak and mean)
 - ii. Quantify severity of mitral regurgitation (ERO, vena contracta width)
 - iii. Left ventricular outflow tract (LVOT) width in millimeters (mm) and gradient
 - iv. Presence of other valvular heart disease
 - v. Left ventricular ejection fraction
 - 2. To be collected following placement of valve:
 - i. central or paravalvular mitral regurgitation
 - ii. transmitral gradient
 - iii. left ventricular outflow tract (LVOT) gradients
- B. Cardiac output and cardiac index
- C. Adverse Event Assessment

14.4 Discharge Procedures

The following data will be collected for all study subjects within 24 hours of the date of discharge from the index hospitalization. However, subjects discharged within 48 hours of exiting the cath lab / operating room are not required to repeat tests collected during the Post Procedure period that are also required for the discharge visit. See Table 1.0. If subject is discharged over a weekend or holiday, the discharge tests may be completed on the last weekday prior to discharge.

A. Systems:

- 1. Pertinent physical examination [includes blood pressure, height, weight, major systems findings] including clinical assessment for Stroke and/or TIA;
- 2. Medications given for cardiovascular effect including anti-platelet/anti-thrombins;
- 3. Adverse Event assessment;

B. Cardiac:

- 1. Transthoracic echocardiogram (TTE).
- 2. NYHA classification;
- 3. Standard 12-lead ECG;
- 4. Chest X-ray examination

C. Clinical Laboratory Tests:

- 1. B-type natriuretic peptide (BNP).
- 2. CBC and platelet count;
- 3. PT/INR;
- 4. Metabolic Panel

14.5 Follow-Up Procedures

Follow-up procedures will be conducted at the intervals specified in Table 1.0. Blood draws will be performed at the specified intervals and according to hospital standard or medication regimen. Subjects will be informed that some of the data that are collected at scheduled followups as well as at unscheduled visits, including the echocardiogram and CT scan may be sent to the respective independent core lab for analysis.

If a subject cannot be reached for a follow-up visit, the investigator will document on the followup data form, the efforts undertaken to contact the subject. These efforts should include 3 attempts of telephone contacts at separate dates and times, and a registered letter. If the subject cannot be reached in any way for their follow-up visits and misses the scheduled visit, new efforts will be undertaken to locate them at subsequent follow-up visits. In the event that the subject's implanted value is explanted, the subject needs to be continued to be followed for the duration of the study.

Follow-up visit intervals are as follows: 30 days (-7/+14 days), 6 months (±30 days), 12 months (+60 days). Additional phone follow-ups may be performed as needed to obtain up to date survival information for use in regulatory submissions.

For all subjects at all visits, the time clock starts on the date of the first implant attempt, whether or not the implant is successful and site visits will be scheduled accordingly.

14.4.1 One Month Follow-Up Visit

The following data will be collected for all study subjects at one month (within 7 days before and 14 days after the 30 days date)

A. Systems:

- 1. Pertinent physical examination [includes blood pressure, height, weight, major systems findings] including clinical assessment for Stroke and/or TIA;
- 2. Medications given for cardiovascular effect including anti-platelet/anti-thrombins;
- 3. Adverse Event assessment

B. Cardiac:

- 1. 4D Computed Tomography scan with contrast of the heart to include valve assessment
- 2. NYHA classification
- 3. Standard 12-lead ECG
- 4. Transthoracic echocardiogram (TTE)

C. Functional Assessments:

- 1. 6MWT
- 2. QOL: KCCQ

D. Clinical Laboratory Tests:

1. CBC and platelet count

- 2. Complete Metabolic Panel (CMP)
- 3. B-type natriuretic peptide (BNP)
- 4. Plasma free hemoglobin
- 5. Haptoglobin
- 6. PT/INR

E. Non-Invasive Studies:

1. Chest X-ray examination

14.4.2 Six Month Follow-Up Visit

The following data will be collected for all study subjects at 6 months: (±30 days).

A. Systems:

- 1. Pertinent physical examination [includes blood pressure, weight, major systems findings] including clinical assessment for Stroke and/or TIA;
- 2. Medications given for cardiovascular effect including anti-platelet/anti-thrombins;
- 3. Adverse Event assessment

B. Cardiac:

- 1. 4D Computed Tomography scan with contrast of heart to include valve assessment *if* any of the following have occurred:
 - A. presence of thrombus on 30 day 4DCT scan
 - B. Increase in mitral gradient as measured on TTE
 - C. Clinical deterioration or clinical event including:

i. neurological or peripheral embolic event

- ii. Rehospitalization for heart failure
- 2. NYHA classification
- 3. Transthoracic echocardiogram (TTE)

C. Clinical Laboratory Tests:

- 1. Plasma free hemoglobin
- 2. Haptoglobin
- 3. PT/INR (if applicable)

February 26, 2016 Protocol Version 1.1

14.4.3 Twelve Month Follow-Up Visit

The following data will be collected for all study subjects at 1 year (365 days) +60 days.

A. Systems:

- C. Pertinent physical examination [includes blood pressure, weight, major systems findings] including clinical assessment for Stroke and/or TIA;
- D. Medications given for cardiovascular effect including anti-platelet/anti-thrombins
- E. Adverse Event assessment

B. Cardiac:

- F. NYHA classification
- G. Standard 12-lead ECG
- H. Chest X-ray examination
- I. Transthoracic echocardiogram (TTE)

C. Clinical Laboratory Tests:

- J. CBC and platelet count
- K. Complete metabolic panel
- L. B-type natriuretic peptide (BNP)
- M.Plasma free hemoglobin
- N. Haptoglobin.
- O. PT/INR (if applicable)

D. Functional Assessments:

- P. 6MWT
- Q. QOL: KCCQ

SITRAL

Baylor Scott & White Research Institute 15.0 STUDY DATA MONITORING AND DATA AND SAFETY MONITORING BOARD

The purpose of the monitoring plan is to facilitate compliance with GCP guidelines (GCP 5.18.1), FDA guidelines and FDA regulations (21 CFR 812). The monitoring plan for this study includes use of monitoring services and institution of a Data and Safety Monitoring Board. A Data Safety and Monitoring Board (DSMB) will be constituted for this study to provide additional safety review. The DSMB is an independent advisory group of experts with a mandate to periodically review and evaluate safety and evaluate data for continuing validity.

The DSMB will be responsible for assuring that research subjects are not exposed to unnecessary or unreasonable risks. Ongoing responsibilities of the DSMB will be to evaluate the progress of the study, including periodic assessments of adverse events and serious adverse events. The DSMB will report on the safety and scientific progress of the study.

On site monitoring will be completed at regular intervals at each site commensurate with enrollment of the first subject and completion of the index procedure. As an electronic data capture system will be used to collect the data, the data entered into the database will be remotely reviewed to evaluate for potential safety issues such as unanticipated adverse device effects. Compliance with the study milestones for each enrolled subject will be reviewed, as well. Sites will be contacted for source information as indicated.

Reports from each monitoring visit will be provided to the site Investigator and the sponsor at completion of the monitoring.

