19.0 DEVIATIONS FROM THE STUDY PROTOCOL

The Investigator will not deviate from the protocol without the prior written approval of the Sponsor except in medical emergencies or in unforeseen, isolated instances where minor changes are made that will not increase the subject's risk or affect the validity of the study. Any subsequent revisions to the

Confidential

protocol, including the Informed Consent Form and the Case Report Forms, other than very minor revisions, must be approved by the Sponsor, the FDA, and the IRB. In medical emergencies, prior approval for protocol deviations will not be required, but the Sponsor or its designee and IRB must be notified within 5 working days of the incident. Periodic monitoring of protocol compliance will be performed for each site. Deviations will be documented on the appropriate case report form. The sponsor has the right to suspend enrollment at sites deemed to have excessive protocol compliance issues.

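### DSMB review is tied to neither deaths nor subjects treated, and deaths have no stated route to the board, so no pre-set pause is required before all 30 subjects are treated

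*Combined protocol and SAP*

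**What the plan says.** Section 15.0 describes the board and its remit: "The DSMB is an independent advisory group of experts", "with a mandate to periodically review and evaluate safety and evaluate data for continuing validity". It adds a broad duty: "The DSMB will be responsible for assuring that research subjects are not exposed to unnecessary or unreasonable risks". The content of review is stated as "including periodic assessments of adverse events and serious adverse events". The section gives no meeting interval, no count of subjects or deaths that prompts a review, and no rule for pausing.

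The other relevant places are these:

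- **Section 4.0:** "The study cohort will comprise all consecutive subjects undergoing mitral valve replacement" at several centers; the cohort "will consist of up to 30 subjects". There is no staging and no enrolment hold.
- **Section 9.0:** a subject counts as enrolled at skin incision, so every enrolled subject is exposed to the operation. Case review checks each candidate's eligibility, not accumulating outcomes.
- **Section 22.7 and Table 1.0 (investigator report requirements):** serious events go to the sponsor and IRB. The DSMB is not listed as a recipient.
- **Section 19.0:** "The sponsor has the right to suspend enrollment at sites deemed to have excessive protocol compliance issues". This is the only enrolment suspension that the text spells out, and it concerns compliance.
- **Section 23.0:** descriptive statistics only, with no interim look.
- **Section 1.0:** the related, mainly transseptal experience had LVOT obstruction, valve embolization "and a 30-day mortality (34%) in the limited data available".

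**The concern.** The study is meant to improve on an approach whose cited early mortality is 34%, and it rests its own approach on 3 treated subjects. A poor early result is therefore a realistic possibility. In a cohort of 30, the value of a safety board depends on when it looks and on what makes it look. A board that meets at unspecified times, and that is not a named recipient of death reports, could meet its written obligations and still first see the deaths after most subjects have had the operation. What is at stake is avoidable exposure, not the validity of an estimate.

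**Working it through.** The plan has no figure to reproduce: it states no interim look, boundary or derivation of the 30. The check has three parts.

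**1. Would an early excess be visible?** Inputs: N = 30 (Section 4.0) and 34% (Section 1.0), used for scale only. Expected deaths are 30 × 0.34 = 10.2. Exact binomial tails:

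| Event | true 34% | true 10% |
|---|---|---|
| ≥2 deaths in first 5 | 55.2% | 8.1% |
| ≥4 in first 10 | 45.9% | 1.3% |
| ≥5 in first 15 | 61.7% | 1.3% |

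A high rate would often show by 10 to 15 subjects. Nothing in the text requires a review then.

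**2. Could all 30 be treated before the first meeting?** Neither accrual nor the meeting interval is given, so both are assumed. If the first meeting falls at 3, 6 or 12 months, all 30 are already treated when accrual is at least 30/3 = 10, 30/6 = 5 or 30/12 = 2.5 subjects per month across sites. It can happen; whether it would is unknown.

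**3. What would a pre-set pause do?** The illustrative rule uses a flat Beta(1,1) prior and flags when the posterior probability that 30-day mortality exceeds 34% is above 0.90. With k deaths in n subjects this probability equals P(Binomial(n+1, 0.34) ≤ k).

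- 3 deaths in 4: 0.951, flag. 3 in 5: 0.893, no flag.
- 2 deaths in 2: 1 − 0.34³ = 0.961, flag. The start of monitoring therefore has to be stated.

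Applied after each subject from the third, the boundary is 3 deaths in 4 or fewer, 4 in 7, 5 in 9, 6 in 11, 7 in 14, 8 in 16, 9 in 18, 10 in 21, 11 in 23, 12 in 26, 13 in 28 and 14 in 30.

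Pause probabilities come from the exact recursion q_n(k) = (1−p)·q_{n−1}(k) + p·q_{n−1}(k−1), removing paths that reach the boundary:

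| True 30-day mortality | P(pause), from n = 3 | P(pause) if 2 in 2 also counts |
|---|---|---|
| 10% | 0.6% | 1.4% |
| 15% | 2.2% | 3.7% |
| 20% | 5.8% | 8.0% |
| 34% | 35.1% | 37.8% |
| 50% | 86.1% | 86.8% |

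Expected deaths with the n = 3 start, if a pause ended enrolment and each outcome were known before the next operation, equal p times expected subjects treated. At 34% this is 0.34 × 22.8 = 7.7, against 10.2. At 50% it is 0.50 × 12.1 = 6.0, against 15. The 6.0 is a total over all runs: 0.861 × 5.2 for runs that pause plus 1.56 for runs that never do. If 3, 5 or 10 more subjects were treated after the boundary was reached (assumed lags), the 6.0 would become about 7.3, 8.1 or 10.1.

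**Sensitivity to the reference rate.** With looks after 5, 10, 15, 20 and 25 subjects, the same 0.90 cut-off and a Beta(p0, 1−p0) prior, a 20% reference flags in 73.4% of trials when true mortality is 34%, and a 34% reference in 19.7%. When true mortality is 10%, the figures are 2.0% and 0.1%.

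**The case against.** The strongest reply is that subjects are not unprotected. The DSMB has a general duty on unreasonable risk, its review covers serious events, data are reviewed remotely for safety, and deaths reach the sponsor and IRB within days. Table 1.0 also contemplates withdrawal of IRB approval. All of this stands. A reader might infer that a pre-set rule would be the only protection, or that compliance is the only ground on which the trial could be halted. The documents do not support either. They leave room for an ad hoc pause; they just do not require one, and they do not put the deaths in front of the board. A charter with triggers may also exist, but none is cited.

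On reporting speed, Death appears in the list of anticipated events in Section 22.9. If that list is what the reporting rule means by protocol-defined events, a death follows the 10-working-day route and not the 24-hour one. Neither route names the DSMB.

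A second reply is that the benefit of a boundary is easily overstated. This also stands. A reader might take 15 deaths against 6 as the saving. That contrast assumes 50% mortality, which nothing in the documents suggests, and treats a review pause as permanent. At the cited 34%, expected deaths fall only from 10.2 to 7.7, and about 65% of trials would never pause. The 34% itself comes from a different approach with no stated denominator.

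**Conclusion.** The point holds as a gap in required monitoring, and it should be closed. Followed exactly, the plan allows up to 30 subjects to be operated on without any review being required by the number treated or by accumulating deaths. It does not follow that the board would fail to act, or that all 30 would in fact be treated before its first meeting; that depends on an accrual rate and meeting interval the documents do not give.

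The size of the gain depends on the true mortality and on the rule chosen. The pause probabilities are exact for the illustrative boundary with the n = 3 start. The expected-death figures are upper limits on its benefit, because they assume immediate outcomes and no resumption. The 34% is a benchmark, not a predicted rate for this operation.

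**What to change.** Add to Section 15.0 and Section 22.7, and carry into Table 1.0:

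1. Every death is sent to the DSMB as it is reported.
2. Enrolment at all sites pauses for DSMB review when deaths within 30 days reach a stated boundary. This is a pause for review, not an automatic stop.
3. The sponsor and DSMB confirm the reference rate, the cut-off and the boundary before the first subject, with pause probabilities over a range of true mortality.

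The boundary in the working can serve as a starting point. If it is used, the text must say that monitoring starts at the third subject, or else add 2 deaths in 2 and quote the second set of probabilities.

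The cost is a short paragraph in Section 15.0, a line in Section 22.7 and matching text in the DSMB's operating rules. The board already exists and no subjects are added. The downside is a small chance of an unneeded pause: with the n = 3 start, 0.6% at 10% mortality and 5.8% at 20%.
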